11.2 Statistical Methods for Primary and Secondary Endpoints

Descriptive summary statistics (e.g. means and standard deviations, or median with inter-quartile, as appropriate) will be used to summarize the primary and secondary endpoints by study treatment. The primary and secondary efficacy endpoints will also be analyzed using appropriate models.

The primary endpoint, change in the oxygenation index over time, will be compared between treatment conditions using a linear mixed-effects regression model. The model will be estimated using likelihood estimation which will allow the inclusion of all collected data, regardless of the number of assessments available for assessment. Terms in the model will include the two stratification variables, treatment condition (active or placebo), time of assessment, condition-by-time, recruitment site and a site-by-treatment interaction term. A test of the treatment condition will directly test the main research question. Covariates identified by preliminary analysis as potentially confounding due to baseline differences will be added to the model.

The data analysis plan for secondary efficacy and safety endpoints has been provided in the Statistical Analysis Plan.

The primary and secondary endpoints (including clinical and biological data) will be adjusted for COVID-19 infection as a cause of ARDS, which is adjudicated by the study physicians.

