10 SAMPLE SIZE DETERMINATION

The sample size for this trial will be 60 patients in the hMSCs arm and 60 patients in the placebo arm, for a total of 120 patients with a balanced randomization of patients with $\text{PaO}_2:\text{FiO}_2 < 150$ mmHg. This sample size was determined on the basis of feasibility.

Given the sample size of 60 per treatment condition, in this multisite, randomized trial using oxygenation index as the primary outcome and measures taken at 6 time points, it is estimated the study will have 80% power to detect a difference between conditions for an effect size as low as 0.43. Using the pilot data from Day 4, for example, this would translate to approximately a difference of 1.29 in the oxygenation index.

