12.5 General Methodology

Study Investigators, Study Coordinators, Data Manager and Statistician will be blinded to treatment assignment (randomization assignment will be coded as A group vs. B group) during the study prior to data lock.

Parameters ascribed to the safety and efficacy of patients will be summarized by modified ITT population defined in Section 11.

Continuous variables will be summarized using tables of descriptive statistics: number of patients with recorded observations, mean, standard deviation, median, minimum, maximum and interquartile range (IQR). Comparison of continuous parameters between two groups will be performed using T-test or Wilcoxon-Mann-Whitney test, as appropriate. Categorical variables will be summarized using counts and percentages, and compared between two groups using Pearson's chi-square or Fisher exact test, as appropriate. Based on the data shown in our previous Phase 2a

study, biomarker data will be summarized with descriptive statistics described above on original scale and log-transformed scale.

All statistical tests will be two-sided and will be performed at the 5% level of significance, unless otherwise stated. P-values will be rounded to three decimal places. P-values less than 0.001 will be reported as < 0.001 in tables. In bivariate analyses, P-values will not be adjusted for the comparisons of repeated outcomes between treatment allocations at multiple timepoints. Additional ad-hoc analyses may be conducted as deemed suitable.

As there is a single primary endpoint, and the secondary endpoints are to be used only in providing additional supportive exploratory information, there will be no adjustment for multiple testing.

All outputs will be produced using SAS and STATA (most up to date version available).

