12.6 Analysis for Primary Efficacy Endpoint

The primary endpoint is the changes in the oxygenation index from the baseline to the time-points at 6, 12, 18, 24, 30 and 36 hours after infusion of study product. The oxygenation index will only be calculated when the patient is still being ventilated with positive pressure. If patient is on pressure support, oxygenation index will be treated as missing because the mean airway pressure is not reliable.

Descriptive summary statistics (e.g. means and standard deviations, or median with inter-quartile, as appropriate) will be presented for the oxygenation index values, as well as the changes of oxygenation index from the baseline to each following timepoint by allocated group in modified ITT population.

The change of oxygenation index, by allocated treatment groups in modified ITT Population, will be compared using two linear mixed-effects regression models: unadjusted and adjusted model. Both models will be estimated using maximum likelihood estimation, which will allow the inclusion of all collected data, regardless of the number of assessments available for assessment. All models will include the stratification variables: $\text{PaO}_2/\text{FiO}_2$ ($< 150 \text{ mmHg}$ or $\geq 150 \text{ mmHg}$) and trauma status (trauma vs. non-trauma). Terms in the unadjusted linear mixed-effects regression model will include the two stratification variables, treatment condition (active or placebo), time of assessment (by hour), condition-by-time, recruitment site and a site-by-treatment interaction term. A test of the treatment condition will directly test the main research question. The adjusted linear mixed-effects regression model will include all the variables from the unadjusted model described above plus covariates identified by preliminary analysis as potentially confounding due to baseline differences ($p\text{-value} < 0.20$). The treatment effects may vary with ARDS severity ($\text{PaO}_2/\text{FiO}_2$) or by trauma status, thus the interaction terms will be also included. Both unadjusted and adjusted models will be presented with coefficient with 95% confidence intervals.

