12.8 Adjustments for Stratification and SARS-CoV-2 Infection

Analyses of the outcomes will be adjusted for stratification variables (PaO₂/FiO₂ ratio [<150 mmHg or ≥ 150 mmHg] and trauma vs. non-trauma), APACHE III scores at baseline, and baseline measure, where P-value < 0.20 between treatment group.

To better understand the hMSC effects in patient with COVID-19 disease, the primary and secondary endpoints specified in Section 12.6 and 12.7 will also be summarized and conducted in separate linear mixed-effects regression models, in a fashion parallel to the analyses of the above main primary endpoint models, stratified or adjusted by the following binary variables of interest prior to randomization:

- SARS-CoV-2 infection status obtained from medical chart: yes or no
- COVID-19 as a cause of ARDS which is adjudicated by the study physicians: yes or no
- Viral antigen levels measured by NIH lab (PI: [name]): the value will be categorized by greater or less than median value
- Dexamethasone (or equivalent steroid therapy): yes or no
- Other immunomodulatory agents: yes or no
- Anticoagulation and antiplatelet treatments: yes or no
- MSC viability at the time of administration

Furthermore, the primary and secondary endpoints will be analyzed by latent class analysis (LCA) subphenotype using the same procedures described in previous studies (23-26) and adjusted for SARS-CoV-2 infection. In addition, we will test for an interaction between MSC therapy and the subphenotypes for the clinical outcomes.

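### The single primary endpoint is tested with two unranked models, one built by a p<0.20 imbalance screen, and Protocol 11.2, SAP 12.6 and SAP 12.8 do not agree on the covariates

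*SAP*

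**What the plan says.** - **SAP 12.6.** The change in OI "will be compared using two linear mixed-effects regression models: unadjusted and adjusted model". The unadjusted model holds the two strata, treatment, time in hours, treatment-by-time, site and site-by-treatment. The adjusted model adds baseline variables that differ between arms at p<0.20. The sentence linking the treatment term to the main question follows the unadjusted term list and precedes the adjusted model. Interactions of treatment with P/F severity and trauma are then added, without saying to which model. Both models are to be reported with 95% intervals.
- **Protocol 11.2 (and the synopsis).** One model with the same terms and the same sentence about the treatment test. Then: "Covariates identified by preliminary analysis as potentially confounding due to baseline differences will be added to the model". A later paragraph says the primary and secondary endpoints "will be adjusted for COVID-19 infection as a cause of ARDS, which is adjudicated by the study physicians".
- **SAP 12.8.** Outcome analyses are adjusted for the strata plus "APACHE III scores at baseline, and baseline measure, where P-value < 0.20 between treatment group". Separate models, stratified or adjusted, follow for seven variables, one of them adjudicated COVID-19 cause. They are described as additional and parallel to the main primary-endpoint models.
- **SAP 12.5.** "All statistical tests will be two-sided and will be performed at the 5% level of significance, unless otherwise stated". Because there is one primary endpoint, "there will be no adjustment for multiple testing".
- **SAP 10.** "60 patients in the hMSCs arm and 60 patients in the placebo arm"; "it is estimated the study will have 80% power to detect a difference between conditions for an effect size as low as 0.43".

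**The concern.** The waiver of multiplicity control in SAP 12.5 rests on there being one primary endpoint. That covers one test of the endpoint. It does not cover two models for the same endpoint, each tested at 5%, with no rule for what happens when they disagree.

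The adjusted model has a fault of its own. Its covariates are chosen by testing baseline differences between randomised arms, so its content is unknown until the data are in. The selection also distorts the test. A prognostic variable enters when its chance imbalance is large and stays out when it is small. The left-out variables still inflate the residual variance, but their imbalance has been trimmed, so the standard error is too large for the estimate.

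At stake is whether a reader of the final report can tell if the trial met its primary objective.

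**Working it through.** **1. The plan's own figure.** SAP 10 gives 60 per arm, a standardised effect of 0.43 and 80% power. The raw difference of 1.29 implies an SD of 1.29/0.43 = 3.0. For a single measure, 0.43/√(2/60) = 2.355, and 2.355 − 1.960 = 0.395, which is 65.4% power. For the mean of six measures with within-patient correlation ρ, the variance factor is (1+5ρ)/6. At ρ = 0.65 this is 0.708, and power is 79.9%. The documents state no ρ. I use 0.65 because it reproduces the stated power.

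**2. Simulation of the two SAP 12.6 models.** Assumptions, none given in the documents: patient-level mean OI change, complete data, seven sites of random size, half the patients with P/F below 150, 80% COVID-19, 15% trauma, ten candidate covariates of which four are prognostic and together explain a share R² of the variance. Site-by-treatment is in both models and the treatment term is averaged over sites. The stratum interactions are placed in the adjusted model only. There are 4,000 trials per row. The last column is a model with two prognostic covariates fixed in advance, standing for APACHE III and baseline OI. Entries are percentages of trials significant at 5%, except the opposite-verdict column.

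| True effect, R² | Unadjusted | Screened | Either | Opposite verdicts | Fixed covariates |
|---|---|---|---|---|---|
| 0, 0.1 | 5.3 | 5.0 | 6.6 | 3.0 | 5.3 |
| 0, 0.3 | 5.0 | 3.6 | 6.2 | 3.8 | 5.4 |
| 0, 0.5 | 5.2 | 3.0 | 6.6 | 4.9 | 4.7 |
| 0.43, 0.3 | 72.7 | 74.3 | 79.7 | 12.4 | 78.7 |
| 0.43, 0.5 | 73.1 | 76.9 | 82.2 | 14.5 | 83.6 |
| 0.30, 0.3 | 43.8 | 42.4 | 50.2 | 14.1 | 48.8 |

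Check on the fourth row: both significant = 72.7 + 74.3 − 79.7 = 67.3, so opposite verdicts = 79.7 − 67.3 = 12.4. The Monte Carlo standard error at 5% is √(0.05×0.95/4000) = 0.34 points. If the two tests were independent, the either-model rate would be 1 − 0.95² = 9.75%; correlation brings it down to about 6-7%.

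**3. Wider range.** With 10-40 candidates and R² of 0.2-0.6, a p<0.20 screen picks about 0.20×10 = 2 to 0.20×40 = 8 covariates by chance. A strata-only model was compared with a screened model on one summary value per patient:
- screened model under the null: 1.9-4.2%
- either model under the null: 5.6-7.0%
- opposite verdicts near 80% power: 9-18%

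**4. COVID-19 term.** In the simulation of step 2 at effect 0.43, adding COVID-19 to the unadjusted model moves power from 72.7% to 72.8% (R² 0.3).

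**5. The contrast.** SAP 12.6 does not define the treatment term beside its interactions.
- *Time.* With time linear in hours, the coefficient is the effect at hour 0. The times 6 to 36 have mean 21 and sum of squares 630, so its variance factor is 0.65 + 0.35×(1/6 + 21²/630) = 0.953, against 0.65 + 0.35/6 = 0.708 for the time average. For a constant effect of 0.43, power is 67.4% against 79.9%.
- *Site.* With reference-coded site-by-treatment, the coefficient is the effect at one site, and simulated power is about 17%.

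**The case against.** The strongest defence is that the SAP does settle the choice. The sentence about the main question closes the unadjusted term list, so the unadjusted model is decisive. Both models are pre-specified and both must be shown, which limits selective reporting. SAP 12.3 has the primary analysis run with arms coded A and B. This is a phase 2b trial sized on feasibility, and the null inflation is one or two percentage points.

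Part of this stands. The position of the sentence is a real hint, and the inflation is modest and arises only if the better result is taken. But Protocol 11.2 attaches the same sentence to a model that then receives imbalance-selected covariates, so the two documents point to different models. Showing both does not say which one decides. Coding the arms hides the direction of a difference but not its p-value, so a screen or a choice on p-values remains possible.

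A reader might also infer that the SAP drops the COVID-19 adjustment that the protocol promises. The documents do not support that. SAP 12.8 supplies models for the primary endpoint using adjudicated COVID-19 cause, and Protocol 6.2.3 introduces the COVID-19 analyses as additional work. What is left is a mismatch in standing: Protocol 11.2 states the adjustment without qualification, and the SAP places it outside the two 12.6 models.

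**Conclusion.** The point holds. One endpoint has two unranked tests in SAP 12.6, a differently described single model in Protocol 11.2, and a further covariate set in SAP 12.8. The main consequence is an undefined verdict: near the design effect, roughly one trial in eleven to one in six would be significant by one model and not by the other (9-18%). Either-model rejection of about 6-7% under the null is the smaller harm. The screened test errs on the conservative side, at about 2-4% over the assumed range. It stays close to 5% when the covariates are weakly prognostic (5.0% at R² 0.1).

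All of these sizes depend on the assumed number and strength of candidate covariates, and the simulations ignore missing OI values. The conclusion that no model is named as primary does not depend on them.

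Two stronger readings should be avoided. A reader might infer that the treatment coefficients of the two 12.6 models are different quantities because of the stratum interactions. The SAP does not say whether those terms go in one model or both, so only the ambiguity is established. A reader might also count five rival readings, including the APACHE III and COVID-19 models, which in the simulation gives 8.4-9.2% under the null. SAP 12.8 presents its COVID-19 models as parallel to the main ones, so 6-7% is the fairer figure.

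**What to change.** Before unblinding, amend Protocol 11.2 and SAP 12.6 together, and bring SAP 12.8 into line:

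1. Name one primary model and state that its interval and p-value decide the trial. Fix its covariates in advance: the two strata, site, and collected prognostic baselines such as baseline OI or APACHE III. In the simulation, fixed covariates kept the null rate near 5% and raised power from 72.7% to 78.7% at R² 0.3.
2. State explicitly whether adjudicated COVID-19 cause is in that model, so that both documents say the same. Either answer is workable.
3. Define the decisive treatment contrast, for example the average difference over 6 to 36 hours.
4. Move the site-by-treatment and treatment-by-stratum terms to secondary models, or define the contrast as averaged over them.
5. Delete the p<0.20 screen from SAP 12.6 and 12.8, and the matching sentence from Protocol 11.2 and the synopsis.
6. Label all other models, including the unadjusted one if it is not chosen, as sensitivity analyses.

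The cost is a wording amendment to two documents, with no new data. The team gives up the freedom to adjust the primary result for chance imbalances seen later; those adjustments can still be shown as sensitivity analyses.

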12.2 Randomization, Stratification and Allocation Concealment

After obtaining informed consent from the subject or the subject's legal authorized representative (LAR), the study investigators or coordinators will inform the staff at Bone Marrow Transplant (BMT) Lab by a written document. BMT staffs will use a unique Personal Identification Number (PIN) to access the Clinical Coordinating Center web-based randomization system to input participant details. The randomization will use a computer-generated permuted block design with a 1:1 ratio, and stratified by $\text{PaO}_2:\text{FiO}_2 < 150$ mmHg and the presence or absence of trauma. If a randomized patient does not initiate the study product administration (e.g. study withdrawal, failure to achieve stable baseline, etc), the randomization will be returned to the pools.

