12.7 Analyses for Secondary Efficacy Endpoints

12.7.1 Respiratory Physiology Endpoints

The secondary endpoints, such as acute lung injury score, pulmonary dead space and RALE score, expanded oxygenation index up to 7 days and the reduction in ventilator ratios, will be analyzed by linear mix-effects regression models using the modified ITT population, in a fashion parallel to the analyses of the primary endpoint of oxygenation index. Incidence of barotrauma will be analyzed by mixed-effects logistic regression models using the modified ITT population. Counted measures, such as ventilator free days, will be analyzed using zero-inflated negative binomial models in a parallel fashion as well. Achieving pressure support and second infection endpoint will be analyzed using a logistic regression model.

The acute lung injury score (LIS), pulmonary dead space, chest radiograph assessment of pulmonary edema (RALE score) at days 0, 1, 2, 3 and 7 (5 timepoints) will be summarized in modified ITT population by allocated group.

The reduction in ventilatory ratio at 6, 12, 18, 24, 36 hours from the baseline will be summarized in modified ITT population by allocated group.

The incidence of barotrauma will be categorized as yes or not on days 1, 2, 3 and 7, and summarized by patient counts and percentages. Evidence of barotrauma includes the following:

- Pneumothorax
- Bronchopleural fistula
- Tracheobronchial fistula;
- Pneumomediastinum
- Subcutaneous emphysema
- Pneumoatocoele

Ventilator free-days by 7, 14 and 28 days will be calculated as described in *Section 8.7*. They will be summarized as median and interquartile range by allocated group, separately.

Duration of assisted ventilation over 28 days will be calculated among survivors by day 28. It will be summarized as median and interquartile range.

Achieving pressure support ventilation equal to 5 cm H₂O with positive end-expiratory pressure (PEEP) equal to 5 cm H₂O for 2 hours will be categorized as yes or not, and summarized by patient counts and percentages.

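### Primary mixed models fitted by maximum likelihood with no small-sample degrees of freedom: the nominal 5% test is mildly anti-conservative, by an amount that depends on how site and the treatment contrast are handled

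*SAP*

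**What the plan says.** SAP 12.6 compares the change in oxygenation index between arms with an unadjusted and an adjusted linear mixed-effects model, and says: "Both models will be estimated using maximum likelihood estimation, which will allow the inclusion of all collected data". Protocol 11.2 is less specific: "The model will be estimated using likelihood estimation which will allow the inclusion of all collected data". That wording covers either form of likelihood, so the choice of maximum likelihood (ML) comes from the SAP.

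The unadjusted model contains the two stratification variables, treatment, time in hours, treatment-by-time, recruitment site and site-by-treatment. The adjusted model adds covariates that differ at baseline with p < 0.20. Interactions of treatment with the two strata are also to be included, though the text does not say clearly in which model. SAP 12.8 adds APACHE III and the baseline measure under a similar rule.

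SAP 12.5 sets the error rate: "All statistical tests will be two-sided and will be performed at the 5% level of significance, unless otherwise stated". It names SAS and STATA, but no reference distribution and no degrees-of-freedom method. Several secondary endpoints in SAP 12.7.1 are to be analysed "in a fashion parallel to the analyses of the primary endpoint of oxygenation index".

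The SAP does not say whether the site terms are fixed or random, what the covariance structure is, or whether the treatment test refers to hour 0 or to an average over the 36 hours.

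**The concern.** ML estimates the between-patient variance by dividing a residual sum of squares by the number of patients. REML divides by the number of patients less the number of patient-level fixed effects. With few fixed effects the difference is trivial. Here the site and site-by-treatment terms may use 12 columns on their own, on 120 patients.

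An underestimated variance makes the primary p-value too small and the 95% confidence interval too narrow. This is the trial's single primary endpoint, and its test would not hold the level the SAP declares. The reason the SAP gives for ML, that it uses all collected data, applies equally to REML, so it does not call for ML.

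**Working it through.** **1. The plan's own figure.** The documents give no calculated type I error, only the nominal 5%. The nearest computed figure is the power in SAP 10: "it is estimated the study will have 80% power to detect a difference between conditions for an effect size as low as 0.43", for which "this would translate to approximately a difference of 1.29 in the oxygenation index". The implied SD is 1.29 / 0.43 = 3.0.

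A single-measure comparison with 60 per arm has 65.4% power at 0.43, two-sided. The mean of six measures with intraclass correlation ρ has variance factor (1 + 5ρ)/6. With 60 per arm, 80% power needs a standardised difference of 0.5115. So (1 + 5ρ)/6 = (0.43/0.5115)² = 0.707, and ρ ≈ 0.65. The documents state no correlation, so the 80% cannot be reproduced from stated inputs, but it is consistent with ρ ≈ 0.65. That value is used below as an assumption.

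**2. Patient-level columns.** SAP 10 gives N: "The sample size for this trial will be 60 patients in the hMSCs arm and 60 patients in the placebo arm", so N = 120. SAP 5 gives seven sites.
- Site terms fixed: intercept 1 + strata 2 + treatment 1 + site 6 + site-by-treatment 6 = 16.
- With two stratum-by-treatment interactions: 18.
- With an assumed 0 to 5 data-chosen covariates as well: 18 to 23.
- Site terms not fixed: 1 + 2 + 1 = 4.

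**3. Contrast averaged over time.** In a balanced random-intercept model, SE(ML)/SE(REML) = √((N − p)/N). The size against a normal reference is 2·P(t with N − p df > 1.96 × ratio).

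| p | Ratio | SE too small by | Size, normal reference | Size, t on N − p df |
|---|---|---|---|---|
| 4 | √(116/120) = 0.983 | 1.7% | 5.6% | 5.4% |
| 16 | √(104/120) = 0.931 | 6.9% | 7.1% | 6.8% |
| 18 | √(102/120) = 0.922 | 7.8% | 7.4% | 7.0% |
| 23 | √(97/120) = 0.899 | 10.1% | 8.1% | 7.8% |

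The last column keeps the ML variance and changes only the reference distribution. Most of the excess remains, so the main cause is the variance. If missing values left 100 contributing patients (an assumption), p = 16 gives √(84/100) = 0.917, which is 8.3% too small and a size of 7.6%.

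**4. Contrast at hour 0.** With uncentred hours and treatment-by-time in the model, the treatment coefficient is the effect at hour 0. The times 6 to 36 have mean 21 and sum of squares about the mean 630, and 21²/630 = 0.7. In units of the total variance, the between-patient part is ρ + (1 − ρ)/6 and the part from the slope is 0.7(1 − ρ). ML shrinks essentially only the first part. At ρ = 0.65 these are 0.708 and 0.245, total 0.953.
- p = 16: (0.708 × 104/120 + 0.245)/0.953 = 0.901. The square root is 0.949, so the SE is 5.1% too small. Size ≈ 2·P(Z > 1.96 × 0.949) = 6.3%.
- p = 22: (0.708 × 98/120 + 0.245)/0.953 = 0.864. The square root is 0.929, so the SE is 7.1% too small, with size 6.9%.

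For ρ from 0.4 to 0.9 and p from 16 to 22, the shortfall is 3.8-8.9% and the size 5.9-7.4%.

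**5. Simulation.** About 4,000 null trials per scenario, ρ = 0.65, seven sites, six times. The Monte Carlo standard error is about 0.35 points near 5%. The REML column uses a t reference on N − p df as a stand-in for Kenward-Roger.

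| Scenario | ML, normal reference | REML, t |
|---|---|---|
| p = 16, equal sites, averaged | 7.9% | 5.1% |
| p = 16, unequal sites, averaged | 8.1% | 5.6% |
| p = 16, 25% dropout, averaged | 7.3% | 4.9% |
| p = 22, averaged | 8.0% | 4.6% |
| p = 16, hour 0 | 6.5% | 4.3% |
| p = 22, hour 0 | 7.4% | 5.1% |
| p = 4, no site columns, no true site variance | 6.1% | 4.6% |

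A separate simulation (3,000 runs, ρ = 0.63) with 30% dropout gave ML sizes of 6.7% for the unadjusted model and 8.2% for the adjusted model.

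**The case against.** The strongest reply is that the larger figures depend on choices the SAP does not make. Twelve of the 16 columns come from site terms that the SAP never labels fixed. Without them the size is about 5.6%. The closed form in step 3 assumes a time-averaged contrast, whereas a model with time in hours and treatment-by-time can equally be read as testing hour 0. The number of covariates at the upper end is assumed, and no reference distribution is stated. All of this stands, and the figures are therefore given by reading. Fixed is nonetheless the more natural reading, because the site terms are listed beside strata and treatment and none is called random. Every reading examined errs in the same direction.

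A reader might infer that standard errors are simply 7-10% too small and that the primary test runs at 7-8%. The documents do not support that without conditions: it needs fixed site terms, a time-averaged contrast and, at the top, about five covariates.

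A reader might also infer that every secondary endpoint is affected. SAP 12.7 uses logistic models for barotrauma, pressure support and infection, a zero-inflated negative binomial model for ventilator-free days, and a proportional-odds model for the ordinal scale. The REML argument does not carry over to those. SAP 12.5 also treats secondary endpoints as exploratory, so the consequence there is small.

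Finally, this is a phase 2b trial sized on feasibility, and no bias in the treatment estimate itself is shown. That limits the severity but does not remove the point.

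**Conclusion.** The concern holds in a conditional form. As written, SAP 12.6 understates the variance and does not hold its declared two-sided 5% level.

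- Site and site-by-treatment fixed, averaged contrast: SE about 7% too small, size about 7%, so a nominal 95% interval covers about 93%.
- Same, with stratum interactions and an assumed 0 to 5 covariates: about 8-10%, size 7.4-8.1%.
- Contrast at hour 0, ρ assumed 0.65: size about 6.3-6.9%.
- Site terms not fixed: size about 5.6%. This takes no true site variance and was not worked out for a non-zero site-by-treatment variance.

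The excess over 5% is thus roughly 0.6 to 3 percentage points. It should be fixed because the remedy is simple and the endpoint is primary, but it is not an error that undermines the trial.

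**What to change.** In SAP 12.6, replace maximum likelihood with restricted maximum likelihood with Kenward-Roger (or Satterthwaite) degrees of freedom, for both primary models. In the same sentence, state whether site and site-by-treatment are fixed or random, and whether the treatment contrast is averaged over 6 to 36 hours or taken at a named time. Without these last two statements the test remains undefined even under REML.

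Apply the same estimation rule to the secondary endpoints analysed by linear mixed models: the linear endpoints of SAP 12.7.1, the non-pulmonary SOFA score in 12.7.3 and the biomarkers in 12.7.10. Do not apply it to the logistic, zero-inflated negative binomial or ordinal models. Protocol 11.2 needs no change on estimation, because REML is also a likelihood method.

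The cost is one SAP sentence and a software option, settled before unblinding. No data are lost. P-values and confidence intervals become slightly less favourable; in the simulations the size returned to 4.3-5.6%.
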